## 3.4 Efficacy Assessment

For the efficacy analyses, only the assessments from the evaluable ear will be used.

### 3.4.1 Primary Efficacy Endpoints

#### Primary Analysis

The primary endpoint for efficacy will be the proportion of subjects with therapeutic cure at test-of-cure (Visit 4).

- Therapeutic cure is defined as both mycological cure and clinical cure.

- Mycological cure is defined as eradication (culture does not show growth of any fungal pathogen) or presumed eradication (there is no material to culture and the overall clinical outcome is clinical cure).
- Clinical cure is defined as a TSSS of zero on a 4-point scale for pruritus, otalgia, ear fullness and otorrhea.

Therapeutic cure at Visit 4 will be compared between treatment groups by using a chi-square test, under a two-sided 5% significance level. The 95% confidence intervals together with the p-value based on the normal approximation to the binomial distribution will be presented for the between-treatment group differences in the therapeutic cure rate. For each treatment group, the 95% confidence intervals of the therapeutic cure rate using the Clopper-Pearson method will also be presented.

Patients with missing efficacy data or indeterminate outcomes will be considered as treatment failures for efficacy analyses. Patients who discontinue for lack of efficacy or rescue medication will be considered as treatment failures.

For the main objective of the study, the statistical analysis of the primary endpoint will be performed in the MITT population.

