10.1.10.1 Primary efficacy endpoint

Primary analysis of the primary endpoint

The primary endpoint for efficacy will be the proportion of subjects with therapeutic cure at test-of-cure (Visit 4).

Therapeutic cure is defined as both mycological cure and clinical cure.

Mycological cure is defined as eradication (culture does not show growth of any fungal pathogen) or presumed eradication (there is no material to culture and the overall clinical outcome is clinical cure).

Clinical cure is defined as a TSSS of zero on a 4-point scale for pruritus, otalgia, ear fullness and otorrhea.

Therapeutic cure at Visit 4 will be compared between treatment groups by using a chi-square test, under a two-sided 5% significance level. The 95% confidence intervals based on the normal approximation to the binomial distribution will be presented for the between-treatment group differences in the therapeutic cure rate. For each treatment group, the 95% confidence intervals of the therapeutic cure rate using the Clopper-Pearson method will also be presented.

For the main objective of the study, the statistical analysis of the primary endpoint will be performed in the MITT population.

Secondary analyses of the primary endpoint

The efficacy analyses of the primary endpoint conducted on the MITT population will be repeated on the MPP and CITT populations.

Sensitivity Analyses of the primary endpoint

- The proportion of subjects with therapeutic cure at Visit 4 will be analyzed using the standardized estimator (Steingrimsson, 2017)¹⁶.
- The proportion of subjects with therapeutic cure at Visit 4 will be analyzed using multiple imputation method to define missing data.
- The proportion of subjects with therapeutic cure at Visit 4 will be analyzed using worst case scenario to define missing data, in which missing endpoints for treatment arm patients are set to therapeutic failure and missing endpoints for control arm patients are set to clinical cure.

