### 2.2.4 *Sample Size Determination*

Planned enrollment is 191 patients randomized in 2:1 ratio (Clotrimazole 1% otic solution: Placebo) to obtain 150 evaluable patients (100 Clotrimazole 1% and 50 Placebo) for each trial.

Clotrimazole otic solution should be statistically superior to the placebo ( $p<0.05$ ) with regard to the therapeutic cure at the test-of-cure visit, using the MITT population.

Assuming a significance level of 5% and a desired statistical power of 95%, a placebo effect of 30%, and a 2:1 allocation schedule, the total number of patients needed to detect a difference of 30% in the therapeutic cure (100% relative increase) is 150 (100 with clotrimazole and 50 with placebo). The suspected dropout rate due to negative mycological culture at baseline is 21% that leads to a required inclusion of 191 patients (127 for the clotrimazole group and 64 patients for the placebo group).

As CLEAR-1 and CLEAR-2 are twin trials, if one of them is completed before the other, an updated sample size computation will be performed for the latter in order to have a more accurate picture of treatment and control arm success probabilities.

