### 3.4.3 *Subgroups*

Analyses of primary efficacy variable will be performed for subgroups of patients based on baseline characteristics for the following:

- Age group (<65 years, ≥65 years)
- Sex (male versus female)
- Unilateral/bilateral
- Fungal infection/Fungal and bacterial infection/Bacterial infection

Any additional subgroup may be considered.

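### SAP 3.4.1 attaches to the chi-square primary test an extra normal-approximation p-value whose variance is not defined: it is either redundant or can contradict the test, and a score-type interval would serve better

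*SAP*

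**What the plan says.** SAP 3.4.1 (Primary Analysis) says that therapeutic cure at Visit 4 will be "compared between treatment groups by using a chi-square test, under a two-sided 5% significance level". The next sentence concerns the between-group difference: "The 95% confidence intervals together with the p-value based on the normal approximation to the binomial distribution will be presented". Within each arm the SAP uses Clopper-Pearson intervals. The pairing of interval and p-value returns in SAP 3.4.2, 3.4.2.1 and 3.4.2.2 for the secondary endpoints.

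Protocol 10.1.10.1 names the same test and level, but its corresponding sentence has an interval only: "The 95% confidence intervals based on the normal approximation to the binomial distribution will be presented". SAP section 5, which lists departures from the protocol, does not mention the added p-value.

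Neither document says whether the normal approximation uses a pooled or an unpooled variance. SAP 3.4.3 plans subgroup analyses of the primary variable by age, sex, laterality ("Unilateral/bilateral") and type of infection. It gives no subgroup sizes and no interval method.

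**The concern.** An uncorrected chi-square test on a 2x2 table is the square of a z-statistic with a pooled variance. The usual normal-approximation interval for a difference in proportions has an unpooled variance, and a p-value reported alongside that interval would naturally share it. With 2:1 allocation the two variances differ. The output could then show, for one hypothesis, two p-values on opposite sides of 0.05, or an interval that includes zero beside a significant test.

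The unpooled interval also covers the true difference less often than 95%, and more so as groups get smaller. At stake are the clarity of a borderline primary result and the honesty of intervals in any small subgroup.

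**Working it through.** **Inputs.** Two-sided 5% chi-square test (SAP 3.4.1). Design assumptions from SAP 2.2.4: "a placebo effect of 30%, and a 2:1 allocation schedule", a 30-point difference (so 60% v 30%), 95% power, 100 + 50 evaluable patients, 21% culture-negative at baseline. Subgroup sizes are not in the documents and are assumed below.

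**1. The plan's own figure.** Pooled rate (60 + 15)/150 = 0.50.
- Null SE = √[0.25 × (1/100 + 1/50)] = 0.0866.
- Alternative SE = √(0.24/100 + 0.21/50) = 0.0812.
- Power = Φ[(0.30 − 1.96 × 0.0866)/0.0812] = Φ(1.60) = 94.6%.

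Exact enumeration of the uncorrected chi-square gives 95.0%. Inflation: 100/0.79 = 126.6 and 50/0.79 = 63.3, so 127 + 64 = 191. The stated sizes reproduce. They also point to the uncorrected (Pearson) test: the pooled formula needs 153.4 in total without a continuity correction and 171 with one.

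**2. The two variances.** With difference d, pooled rate p, and arm rates p1 and p2:
- Pooled: z = d / √[p(1 − p)(1/100 + 1/50)]. This z squared is the Pearson chi-square, so a pooled p-value is identical to the test's.
- Unpooled: z = d / √[p1(1 − p1)/100 + p2(1 − p2)/50]. This is the Wald form.

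| Result | d | Pooled SE, z, p | Unpooled SE, z, p | Wald 95% interval (points) |
|---|---|---|---|---|
| 40/100 v 12/50 | 0.16 | 0.0824, 1.94, 0.052 | 0.0778, 2.06, 0.040 | 0.8 to 31.2 |
| 79/100 v 32/50 | 0.15 | 0.0760, 1.97, 0.048 | 0.0792, 1.89, 0.058 | −0.5 to 30.5 |

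The first trial fails its named test but would show an interval excluding zero. The second passes but would show an interval including zero. The interval column does not depend on how the p-value is computed, so an unpooled interval can contradict the test even if the p-value is pooled.

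**3. How often, at 100/50.** Enumerating all 101 × 51 = 5,151 tables, pooled and unpooled disagree at 5% in 86: 50 significant by Wald only and 36 by chi-square only.

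| True rates | Probability of disagreement |
|---|---|
| 60% v 30% (planned) | about 0.01% |
| 30% v 30% | 1.1% |
| 50% v 30% | 0.8% |
| 45% v 30% | 2.2% |
| 40% v 24% | 4.3% |

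At a common rate of 30%, type I error is 5.06% for chi-square and 5.56% for Wald. Over common rates from 20% to 80% the maxima are 5.65% and 5.77%.

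**4. Coverage at 100/50.**

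| True rates | Wald | Newcombe | Miettinen-Nurminen |
|---|---|---|---|
| 60% v 30% | 94.2% | 94.9% | 95.0% |
| 30% v 30% | 94.4% | 94.9% | 94.9% |
| 60% v 60% | 94.5% | 94.8% | 94.9% |

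**5. Coverage in subgroups, if the same interval is used.** Sizes are assumptions. The range is over the three rate pairs in step 4.

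| Assumed size | Wald, 60% v 30% | Wald, range | Newcombe, 60% v 30% |
|---|---|---|---|
| 30/15 | 93.3% | 92.9–93.3% | 95.1% |
| 20/10 | 92.1% | 91.5–92.4% | 94.4% |
| 14/7 | 88.6% | 88.6–90.8% | 95.2% |
| 10/5 | 88.7% | 85.2–88.7% | 94.6% |

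**6. Agreement of the alternatives with the uncorrected chi-square at 100/50.** A score interval without the N/(N−1) variance factor agrees in every table. Standard Miettinen-Nurminen disagrees in 6 tables and Newcombe in 14, against 86 for Wald.

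**7. Effect on the limits.** At 60/100 v 15/50, Wald gives 30 ± 1.96 × 8.12, or 14.1 to 45.9 points. The Wilson limits are 50.2 to 69.1 (60/100) and 19.1 to 43.8 (15/50). Newcombe then gives:
- lower: 30 − √(9.8² + 13.8²) = 13.1;
- upper: 30 + √(9.1² + 10.9²) = 44.2.

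**The case against.** A reader might infer that the plan sets up two rival primary tests, both the p-value and the interval being unpooled. The text does not say so. The 5% level is attached to the chi-square test alone, and the normal-approximation results are only to be presented. With a pooled variance the p-value cannot disagree with the uncorrected chi-square. The phrase may even mean the chi-square p-value named one sentence earlier. Secondary endpoints are declared supportive. All of this stands, and it reduces the p-value problem to one of definition. It does not settle the interval, whose usual form is unpooled.

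A reader might also infer that subgroup intervals will be badly wrong. The documents give no subgroup sizes and do not say that this interval will be used there. Protocol 2.1 describes the disease as mostly unilateral, so the bilateral stratum could be small, but how small is unknown. At an assumed 50/25 the Wald interval still covers 93.5% to 93.8% for the rate pairs used above.

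Finally, not every alternative matches the test perfectly. At 60% v 30%, standard Miettinen-Nurminen contradicts the uncorrected chi-square in about 0.7% of trials, more often than Wald's 0.01%, because its few discordant tables are likelier at those rates. That is fair. Only the score interval without the N/(N−1) factor removes the mismatch entirely.

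**Conclusion.** The point holds as a minor one. The SAP adds a p-value that the protocol lacks, does not define its variance, and does not list it as a change. It is redundant if pooled, and able to contradict the named test if unpooled. The planned trial is barely exposed: disagreement is about 1 in 10,000 at the design rates and reaches a few per cent only for effects near the significance boundary. The interval's shortfall at 100/50 is under one percentage point.

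The disagreement and coverage figures assume the unpooled form for the quantity concerned. The loss of 6 points or more in the smallest subgroups further assumes about 15 to 21 patients and reuse of the interval there. The documents therefore do not support calling the primary analysis unsound, or the subgroup intervals seriously wrong as a matter of fact.

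**What to change.** 1. In SAP 3.4.1, 3.4.2, 3.4.2.1 and 3.4.2.2, delete the normal-approximation p-value. State that the test is the Pearson chi-square without continuity correction and that its p-value is the only one for each comparison.
2. Use a score-type interval for every between-group difference in proportions, and name it explicitly for the SAP 3.4.3 subgroups. The score interval without the N/(N−1) factor agrees exactly with the test; standard Miettinen-Nurminen or Newcombe nearly does.
3. Record the change of interval in SAP section 5, since the protocol also specifies the normal approximation.

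The cost is SAP wording and a change in programming, with no added patients or data. The limits move a little: in the worked case at the planned rates the lower limit falls from 14.1 to 13.1 points and the upper from 45.9 to 44.2, a shift towards zero. Intervals will be wider where observed rates approach 0 or 1, because the Wald width shrinks to zero there.

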#### Sensitivity Analysis

- The proportion of subjects with therapeutic cure at Visit 4 will be analyzed using the standardized estimator (Steingrimsson, 2017).
- The proportion of subjects with therapeutic cure at Visit 4 will be analyzed using multiple imputation method to define missing data.
- The proportion of subjects with therapeutic cure at Visit 4 will be analyzed using worst case scenario to define missing data, in which missing endpoints for treatment arm patients are set to therapeutic failure and missing endpoints for control arm patients are set to clinical cure.
- The proportion of subjects with therapeutic cure at Visit 4 will be analyzed using the last post-baseline observation carried forward (LOCF) method to define missing data.

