- Presumed Eradication if there is no material to culture and the Overall Clinical Outcome is Clinical Cure;
- Persistence if any fungal pathogen cultured at Visit 1 is still present;
- Presumed Persistence: if there is no material to culture or sample was not taken or sample was not shipped to lab and the Overall Clinical Outcome is not Clinical Cure;
- Recurrence: if there is reappearance of the fungal pathogen present at Visit 1 which was eradicated or presumably eradicated at Visit 2;
- Superinfection if a new fungal pathogen not present at Visit 1 is isolated while the initial pathogen is also present (presence of a nonpathogenic organism will not be considered Superinfection);
- Reinfection: if there is isolation of a new fungal pathogen different from the one present at Visit 1 and the initial pathogen is not present; or
- Indeterminate if none of the above definitions are met and the mycological outcome cannot be determined.

For any patient with a culture positive for fungi at Visit 1, mycological outcome at Visit 4 will be classified as:

- Eradication if the culture does not show growth of any fungal pathogen;
- Presumed Eradication if there is no material to culture and the Overall Clinical Outcome is Clinical Cure;
- Persistence if any fungal pathogen cultured at Visit 1 is still present;
- Presumed Persistence: if there is no material to culture or sample was not taken or sample was not shipped to lab and the Overall Clinical Outcome is not Clinical Cure;
- Recurrence: if there is reappearance of the fungal pathogen present at Visit 1 which was eradicated or presumably eradicated at Visit 2 and/or 3;
- Superinfection if a new fungal pathogen not present at Visit 1 is isolated while the initial pathogen is also present (presence of a nonpathogenic organism will not be considered Superinfection);
- Reinfection: if there is isolation of a new fungal pathogen different from the one present at Visit 1 and the initial pathogen is not present; or
- Indeterminate if none of the above definitions are met and the mycological outcome cannot be determined.

Mycological outcome will be determined for each patient for Visit 2, Visit 3 and for Visit 4 after mycological culture results are made available to the Sponsor or designee.

Mycological cure is defined as eradication (culture does not show growth of any fungal pathogen) or presumed eradication (there is no material to culture and overall clinical outcome is clinical cure).

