### 3.1.3 Handling of Dropouts and Missing Data

Patients with missing efficacy data or indeterminate outcomes will be considered as treatment failures for efficacy analyses.

For the primary and secondary endpoints, patients who discontinue for lack of efficacy or rescue medication will be considered as treatment failures.

In cases of missing or incomplete dates (e.g. AE and concomitant medications), the missing component(s) will be assumed as the most conservative value possible. For example, AEs with missing start dates, but with stop dates either overlapping into the treatment period or missing, will be counted as treatment-emergent, taking the worst-case approach. When partial dates are present in the data, both a partial start date and/or a partial stop date will be evaluated to determine whether it can be conclusively established that the AE started prior to the start of study drug or ended prior to the start of study drug. If the above cannot be conclusively established based on the partial and/or present dates, then the AE will be considered as treatment-emergent. Actual data values as they appear in the original electronic Case report form (eCRF) will be presented in the data listings.

Missing values for other variables will not be imputed and only observed values will be used in data analyses and summaries.

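### The worst-case sensitivity analysis sets missing control patients to clinical cure, one of two components of the endpoint, so how far it departs from the primary analysis is undefined

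*SAP*

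**What the plan says.** SAP 3.4.1 defines the endpoint by two conditions: "Therapeutic cure is defined as both mycological cure and clinical cure". Mycological cure is eradication or presumed eradication.

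The primary analysis handles missing data the same way in both arms. SAP 3.1.3, repeated in 3.4.1, states: "Patients with missing efficacy data or indeterminate outcomes will be considered as treatment failures for efficacy analyses".

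The worst-case bullet under Sensitivity Analysis analyses the proportion with therapeutic cure at Visit 4. For the active arm, "missing endpoints for treatment arm patients are set to therapeutic failure". For the placebo arm, "missing endpoints for control arm patients are set to clinical cure". Protocol 10.1.10.1 carries the same rule for both arms.

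The mycological categories for Visit 4 are in SAP 2.3.1.2.1. The only route to mycological cure without a culture result is "Presumed Eradication if there is no material to culture and the Overall Clinical Outcome is Clinical Cure". Presumed Persistence covers more situations, namely "if there is no material to culture or sample was not taken or sample was not shipped to lab", but only when the patient is not a clinical cure. The residual category is "Indeterminate if none of the above definitions are met and the mycological outcome cannot be determined".

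**The concern.** The two halves of the worst-case rule name different endpoints. The active-arm half assigns the therapeutic endpoint. The placebo-arm half assigns only its clinical component and leaves the mycological one unstated.

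This matters because the placebo-arm half is all that separates this analysis from the primary one: missing active-arm patients are already failures there. It is also the only listed analysis built to count missing outcomes against the drug. The primary analysis fails both arms alike, and multiple imputation and LOCF have no fixed direction. If the imputed placebo patients do not become therapeutic cures, a reader could take the result as evidence of robustness that was never tested.

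**Working it through.** **1. The plan's own figure.** SAP 2.2.4 assumes cure rates of 30% and 60%, 2:1 allocation, a 5% level and 95% power, giving 100 + 50 patients. The test is specified in SAP 3.4.1 "under a two-sided 5% significance level". With a pooled rate of (60 + 15)/150 = 0.50:

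- null SE = √(0.50 × 0.50 × (1/100 + 1/50)) = √0.0075 = 0.0866
- alternative SE = √(0.60 × 0.40/100 + 0.30 × 0.70/50) = √0.0066 = 0.0812
- power = Φ((0.30 − 1.96 × 0.0866)/0.0812) = Φ(1.60) = 94.6%

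This agrees with the stated 95%. The inflation also reproduces: 100/0.79 rounds up to 127 and 50/0.79 to 64, total 191. The 100 v 50 layout is used below.

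**2. What happens to a placebo patient whose Visit 4 endpoint is missing.** Three readings of the bullet, applied to three kinds of missing endpoint:

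| Placebo patient at Visit 4 | Strict categories | Missed visit treated as nothing to culture | Bullet means therapeutic cure |
|---|---|---|---|
| Visit missed: no TSSS, no sample | Indeterminate, not a cure | Presumed eradication, cure | Cure |
| TSSS observed as 0, sample lost or not shipped | Indeterminate, not a cure | Indeterminate, not a cure | Cure |
| No-growth culture, TSSS missing | Eradication, cure | Eradication, cure | Cure |

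The first row decides most of the result. On the strict reading, imputing clinical cure excludes Presumed Persistence, and an untaken sample does not satisfy Presumed Eradication. Only Indeterminate is left.

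**3. Size.** The documents give no Visit 4 missing rate, so every missing count here is an assumption. Take the planning rates as the primary result, with missing patients already counted as failures: 60/100 v 15/50. Let m placebo patients have missed Visit 4. The test is the Pearson chi-square without continuity correction:

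χ² = d² / [p̄(1 − p̄)(1/100 + 1/50)], where d = 0.60 − (15 + m)/50 and p̄ = (75 + m)/150.

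For m = 0: 0.30²/0.0075 = 12.0, p = 0.0005. For m = 5: 0.20²/(0.5333 × 0.4667 × 0.03) = 5.36, p = 0.021.

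| m of 50 | Strict reading | Set to therapeutic cure | Difference | χ² | p |
|---|---|---|---|---|---|
| 2 (4%) | 15/50, p = 0.0005 | 17/50 | 26 points | 9.02 | 0.003 |
| 5 (10%) | 15/50, p = 0.0005 | 20/50 | 20 points | 5.36 | 0.021 |
| 7 (14%) | 15/50, p = 0.0005 | 22/50 | 16 points | 3.44 | 0.064 |
| 10 (20%) | 15/50, p = 0.0005 | 25/50 | 10 points | 1.36 | 0.24 |

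Seven is the smallest m at which significance is lost.

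**4. A second assumed case.** Suppose 10% are missing in each arm and the planning rates hold among those observed: 0.60 × 90 = 54 and 0.30 × 45 = 13.5, rounded to 14. The primary analysis and the strict reading both give 54/100 v 14/50, 26 points, p = 0.003. Setting the 5 missing placebo patients to therapeutic cure gives 54/100 v 19/50, 16 points, p = 0.065.

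**The case against.** A reader might go further and infer that this analysis simply repeats the primary one and is not a worst case at all. The documents do not support that, for four reasons.

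- The bullet is labelled a worst case, speaks of missing endpoints, and uses the therapeutic term for the other arm. A slip for therapeutic cure is a natural reading.
- There is an arguable route from clinical cure to therapeutic cure. TSSS of zero implies no otorrhea; under the schedule of observations no culture is attempted when no discharge is present; and clinical cure with nothing to culture is presumed eradication. The route is not airtight, because the schedule counts debris as well as otorrhea as discharge and the SAP lists an untaken sample separately, but it is available.
- Keeping the imputed patient a failure through SAP 3.1.3 applies the primary rule inside an analysis meant to replace it. Applied that way, it would also void multiple imputation and LOCF. This has force. It does not settle the matter, because the definition of therapeutic cure alone, without 3.1.3, gives no cure to a patient whose mycological outcome is Indeterminate.
- A placebo patient with a no-growth culture and a missing TSSS becomes a cure on every reading.

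The objection also rightly notes that the size depends on assumed missingness. At planning rates, with 5 of 50 placebo patients missing, the corrected analysis is still significant.

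What remains is that the text supports more than one program. If the phrase is a slip, it stands in both documents and still needs correcting.

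**Conclusion.** The rule as written names the wrong endpoint for the placebo arm and leaves the mycological component of the imputed patient undefined. It cannot be said that the analysis will equal the primary one. It can be said that the text permits nearly that, and equally permits a true worst case.

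The choice can change what the sensitivity analysis shows. At planning rates it makes no difference to significance with up to 6 of 50 placebo patients missing, and it does from 7 (14%). If 10% are missing in both arms, 5 missing placebo patients are enough. These thresholds rest on the planning cure rates, on 100 v 50 patients in the MITT population, and on all missing placebo endpoints being missed visits. The issue is confined to a sensitivity analysis, but it is the one that tests missing data against the drug, so it should be corrected.

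**What to change.** In the worst-case bullet of SAP 3.4.1, replace clinical cure with therapeutic cure for missing control-arm endpoints. Record this in SAP section 5 as a change from the protocol, since protocol 10.1.10.1 has the same wording. If the database is already locked, document it in the clinical study report, as SAP section 1 provides for later deviations.

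No new rule is needed for patients who discontinued for lack of efficacy or took rescue medication: SAP 3.1.3 already makes them failures, and they stay so.

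The cost is one phrase and one entry in section 5. The worst-case figure may be less favourable to the drug. The primary analysis and the sample size are unaffected.
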